3.3 Study Indication

The indication for this study is the treatment of moderate to severe COVID-19.

SELECTION AND WITHDRAWAL OF PATIENTS

4.2 Exclusion Criteria

22

4.3 Stopping Criteria

All AEs should be considered related to study drug unless clearly unrelated or if there is a clear etiology other than study drug such as a pre-existing medical condition, underlying disease, or concomitant medication.

4.3.1 Criteria for Discontinuation of Dosing in Individual Patients

Patients will be discontinued from dosing but will continue to be followed in the study if they experience any of the following:

- \geq Grade 3 (CTCAE v5.0) AE or clinically significant laboratory abnormality considered related to study drug;
- \geq Grade 3 (CTCAE v5.0) infusion reaction in the first 24 hours post-infusion;
- \geq Grade 2 (CTCAE v5.0) cytokine release syndrome;
- \geq Grade 2 skin-related AEs;
- Severe anaphylactic reaction, including bronchospasm; and/or
- Progression to acute respiratory distress syndrome.

For any patient who prematurely discontinues from study treatment, the reason and date of discontinuation will be documented in the electronic case report form (eCRF) and the patient should continue study visits and procedures as outlined in the Schedules of Procedures ([Appendix A](#)).

4.3.2 Criteria for Study Termination

In the event that any of the following are encountered, the DMC will convene as soon as possible to determine if the study must stop enrollment:

- SAE considered related to study drug;
- \geq Grade 3 (CTCAE v5.0) reaction considered related to study drug;
- ≥ 2 patients are discontinued from treatment for safety reasons pertaining to study drug per DMC decision;

- ≥ 2 patients experience similar SAEs or Grade 3 (CTCAE v5.0) AEs related to study drug per DMC decision; and/or
- ≥ 2 patients experience worsening of cytokine release syndrome related to study drug per DMC decision.

The following will not be considered as criteria for study termination:

- Grade 3 to 4 fever if present at study entry;
- Grade 3 nausea if it resolves to \leq Grade 1 within 72 hours;
- Grade 3 fatigue, malaise, or insomnia if it resolves to \leq Grade 1 within 72 hours; and/or
- \leq Grade 4 isolated electrolyte abnormalities that resolve with or without intervention to \leq Grade 2 within 72 hours.

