3 STUDY DESCRIPTION

3.1 Summary of Study Design

This is an interventional, multicenter, 2-arm, parallel-group, randomized, double-blind, placebo-controlled, dose-escalation, safety and efficacy study of F-652 treatment versus placebo in patients aged 18 years or older with a COVID-19 diagnosis confirmed by polymerase chain reaction (PCR). Eligible patients will have moderate to severe COVID-19 symptoms and will be hospitalized. Figure 1 provides an overview of the study design.

AE = adverse event; COVID-19 = coronavirus disease 2019; ECG = electrocardiogram; NIAID = National Institute of Allergy and Infectious Diseases; PCR = polymerase chain reaction; PD = pharmacodynamic(s); SAE = serious adverse event; SARS-CoV-2 = severe acute respiratory syndrome coronavirus 2; TEAE = treatment-emergent adverse event.

The study plans to include 4 cohorts (see [Table 1](#)), with enrolled patients being randomized 1:1 in a blinded manner on Day 1, following screening, to F-652 or placebo as follows:

- Cohort 1 (sentinel cohort): Four patients will receive either [REDACTED] or placebo. Two patients will receive F-652 and 2 patients will receive placebo. Upon completion of sentinel dosing (7 days after last patient last dose), the Data Monitoring Committee (DMC) will evaluate the safety and tolerability data of the sentinel patients and determine if it is acceptable to dose the remaining patients in this dosing group in Cohort 2.
- Cohort 2: Fourteen patients will receive either [REDACTED] or placebo. Seven patients will receive F-652 and 7 patients will receive placebo. Upon completion of Cohort 2, the DMC will convene and review all available safety data to determine if the study can proceed to the next dose level.

- Cohort 3 (sentinel cohort): Four patients will receive either [REDACTED] or placebo. Two patients will receive F-652 and 2 patients will receive [REDACTED]. Upon completion of sentinel dosing (7 days after last patient last dose), the DMC will evaluate the safety and tolerability data of the sentinel patients and determine if it is acceptable to dose the remaining patients in this dosing group in Cohort 4. [REDACTED]
- Cohort 4: Sixteen patients will receive either [REDACTED] or placebo. Eight patients will receive F-652 and 8 patients will receive placebo. [REDACTED]

Table 1. Dosing Strategy

Cohort	Number of Patients	Dosing
1 (sentinel)	4	[REDACTED]
2	14	[REDACTED]
3 (sentinel)	4	[REDACTED]
4	16	[REDACTED]

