8 SAFETY ASSESSMENTS

8.1 Safety Endpoints

The safety endpoints include the following:

- All cause TEAEs and SAEs;
- Change from screening (baseline) in clinical symptoms and abnormal vital signs, abnormal laboratory tests (e.g., complete blood count [CBC], serum chemistry, routine urinalysis, and coagulation function), and 12-lead electrocardiograms (ECGs); and
- Relationship of any observed AEs with F-652 treatment based on the Investigator's judgement.

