Events of progression of the patient's underlying COVID-19 diagnosis will be captured as efficacy endpoints; therefore, events clearly related to progression of the patient's underlying COVID-19 (signs/symptoms of progression) should not be reported as an SAE unless considered related to the study drug or the outcome is fatal during the study or within the safety reporting period. If the event has a fatal outcome during that timeframe, the event of "Progression of COVID-19" must be recorded as an SAE with a fatal outcome.

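### On their natural reading, all five DMC triggers in Section 4.3.2 require attribution to study drug, so deaths attributed to COVID-19 may meet no readable trigger, notably in Cohort 4

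*Combined protocol and SAP*

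**What the plan says.** Section 4.3.2 (Criteria for Study Termination) names five events after which the DMC meets as soon as possible to decide whether enrolment must stop:

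1. an "SAE considered related to study drug";
2. at or above a "Grade 3 (CTCAE v5.0) reaction considered related to study drug";
3. two or more "patients are discontinued from treatment for safety reasons pertaining to study drug per DMC decision";
4. two or more "patients experience similar SAEs or Grade 3 (CTCAE v5.0) AEs related to study drug per DMC decision";
5. two or more patients with worsening cytokine release syndrome, again related to study drug and subject to DMC decision.

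Section 4.3 treats adverse events as related unless they are clearly unrelated or there is "a clear etiology other than study drug such as a pre-existing medical condition, underlying disease, or concomitant medication".

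Section 8.2.3 asks the investigator for a yes/no causality call. Yes requires compatible timing and no other identifiable cause. No requires that timing excludes the drug and that another cause is suspected.

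Under Section 8.3, progression of COVID-19 is generally kept out of SAE reporting. If fatal, it "must be recorded as an SAE with a fatal outcome". Section 8.1 gives the first safety endpoint as "All cause TEAEs and SAEs".

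Section 3.1 and the synopsis schedule a DMC review after each of Cohorts 1, 2 and 3. At the one after Cohort 3 the DMC is to "determine if it is acceptable to dose the remaining patients in this dosing group in Cohort 4". No review is readable for Cohort 4. Section 9.2.4 plans no interim analysis.

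**The concern.** If F-652 made COVID-19 worse, the harm would look like the disease under treatment. A blinded investigator assessing one patient has a ready alternative explanation for each such death. The pattern would show mainly in a comparison of deaths between arms, and no readable item in Section 4.3.2 calls for that comparison.

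What is at stake is timing. An excess of deaths attributed to COVID-19 could wait until the next scheduled review. In Cohort 4, which holds most of the patients at the second dose level, no later review is readable.

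**Working it through.** **Reading the triggers.** Items 1 and 2 say that the event is considered related, item 3 that it pertains to study drug, and items 4 and 5 that it is related. That is 5 of 5 on the natural reading. In item 4 the word *related* could govern only the Grade 3 AEs and not the similar SAEs, which would make it 4 of 5. Items that use all-cause deaths or a difference between arms: 0 of 5.

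**Following a fatal COVID-19 progression through the text.**
- Section 8.3: it is recorded as an SAE, and nothing there makes it related.
- Section 4.3: the presumption of relatedness falls away if underlying disease is a clear cause.
- Section 8.2.3: Yes is unavailable once another cause can be identified.
- Section 4.3.2, item 1: not met if the death is judged unrelated. Item 4: met only if the DMC judges the deaths related, or if *related* does not govern SAEs.

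Sections 4.3 and 8.2.3 also set different standards. A death with compatible timing and COVID-19 as a possible but not clear cause is related under 4.3. Under 8.2.3 it fits neither category: another cause can be identified, so it is not Yes, and timing does not exclude the drug, so it is not No.

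**Coverage by scheduled reviews** (cohort sizes from Sections 3.1 and 9.2.5).
- Total: 4 + 14 + 4 + 16 = 38, which reproduces the planned size.
- On F-652: 2 + 7 + 2 + 8 = 19.
- F-652 patients in cohorts followed by a readable review: 2 + 7 + 2 = 11 of 19.
- Cohort 4: 16/38 = 42% of all patients and 8/19 = 42% of those on F-652.
- Second dose level (Cohorts 3 and 4): 2 + 8 = 10 on F-652, of whom 2 are in a cohort followed by a readable review.

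**Illustration in Cohort 4, 8 versus 8.** Suppose five deaths, all on F-652. Given five deaths among 16 patients, the probability of that split is C(8,5)/C(16,5) = 56/4368 = 0.0128. The mirror-image split is equally likely, so the two-sided Fisher p = 2 × 0.0128 = 0.026. The p-value shows how marked the split is. It does not bear on whether a review would happen, which depends on the wording alone.

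**How likely are several deaths?** P(at least 2 among 8) = 1 − (1 − p)^8 − 8p(1 − p)^7. Section 1.1 gives 6.2% mortality, but for all confirmed cases worldwide. The documents give no figure for hospitalised patients, so the other values are assumptions.

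| Assumed mortality | P(at least 2 of 8) |
|---|---|
| 6.2% | 0.084 |
| 10% | 0.187 |
| 20% | 0.497 |
| 30% | 0.745 |
| 40% | 0.894 |

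**The case against.** A reader might infer that no excess of deaths, however extreme, could ever convene the DMC. The documents do not support that, for four reasons.

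- The contents list Section 3.2 on the DMC and Section 3.2.1, Criteria for Data Monitoring Committee Review. Neither is in the public text, and 3.2.1 may contain a trigger free of causality. The Cohort 4 bullet in Section 3.1 ends in a redaction. The synopsis bullet shows no review and no redaction after its last sentence, but a synopsis is a summary.
- A reader might also infer that a blinded investigator alone decides. Items 3 to 5 leave the judgement to the DMC. Two fatal progressions recorded under one term could be called similar SAEs under item 4, and on its looser reading they would convene the DMC outright.
- Attribution does not all run one way. Section 4.3 lifts the presumption only for a clear other cause, Section 8.2.1 counts a relationship that cannot be ruled out, and the No category in Section 8.2.3 is also strict.
- Deaths known by the time of the reviews after Cohorts 1 to 3 can be seen there; the review after Cohort 2 takes in all available safety data. An excess pooled over all 19 F-652 patients would therefore not go wholly unreviewed.

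It can also be said that an all-cause endpoint governs what is reported, while Section 4.3.2 governs urgent meetings, so the two need not match. That is fair: the difference is a design choice, not a contradiction. Section 4.3.1 likewise stops an individual's dosing for progression to ARDS whatever the cause, and such cases can feed item 3 if the DMC links them to the drug.

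What remains is that a decision by the DMC presupposes a DMC already looking, and that no readable item brings all-cause deaths by arm before it.

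**Conclusion.** The point holds in limited form. On their natural reading all five triggers in Section 4.3.2 need attribution to study drug, and the attribution rules allow COVID-19 to stand as the other cause. Deaths so attributed may meet no readable trigger.

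The exposure is the time between scheduled reviews and, on the readable text, Cohort 4: 16 of 38 patients and 8 of the 10 F-652 patients at the second dose level. The 5/8 versus 0/8 example rests on three assumptions: every death is attributed to COVID-19, *related* in item 4 governs SAEs as well, and Section 3.2.1 holds no causality-free criterion. The last cannot be checked here, so confidence is medium. This is an inexpensive improvement to patient protection, not proof that monitoring is absent.

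**What to change.** Reconcile Section 4.3.2 with Sections 3.2.1, 8.1 and 8.3 so that the DMC reviews cumulative all-cause deaths by randomised arm, without dependence on investigator causality and including during Cohort 4. If Section 3.2.1 already provides this, a cross-reference in 4.3.2 is enough. State in the DMC charter that the committee sees these counts by arm, since the readable text does not say whether it is unblinded.

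Two wording repairs belong with this: reconcile the attribution standards in Sections 4.3 and 8.2.3, and make clear in item 4 whether *related* governs the similar SAEs.

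The change only brings data to the DMC and sets no stopping rule. Any count, threshold or resulting action is for the sponsor and DMC to set. The existing five items stay.

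Cost: a line or cross-reference in 4.3.2, an entry in the charter, and the wording repairs. No new data are needed, because fatal events are already SAEs reported within 24 hours under Section 8.4. The downside is possibly an extra DMC call for deaths that prove balanced between arms.

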APPENDIX C: DEFINITIONS AND MANAGEMENT OF INFUSION-RELATED REACTIONS

In the event of infusion-related reactions, Investigators should institute treatment measures according to best medical practice. Any event of infusion-related reaction, generally defined as clinically significant deviations in blood pressure, heart rate, respiratory rate, and oxygen saturation, will be recorded.

In the event of infusion-related allergic reaction, and if flushing, sudden rash, or difficulty breathing occur, the infusion will be stopped immediately and affected patients will be monitored until the infusion-related allergic reaction has resolved.

The following treatment guidelines may be employed at the discretion of the treating physician:

- Grade 1 infusion-related reaction (Common Terminology Criteria for Adverse Events [CTCAE] v5.0): Mild transient reaction; infusion interruption not indicated; intervention not indicated;
- Grade 2 infusion-related reaction (CTCAE v5.0): Therapy or infusion interruption indicated, but responds promptly to symptomatic treatment (e.g., antihistamines, non-steroidal anti-inflammatory drugs, narcotics, intravenous [IV] fluids); prophylactic medications indicated for ≤ 24 hours;

Treatment of Grade 1 or Grade 2 infusion-related reactions:

1. Decrease infusion rate by 50%, administer antihistamines, corticosteroids, etc., as medically indicated and monitor for worsening condition;
2. Stop infusion if infusion-related symptoms continue despite number 1;
3. Administer bronchodilators, oxygen, antihistamines, corticosteroids, etc., as medically indicated;
4. Resume infusion at 50% of previous rate once reaction has decreased to Grade 1 in severity. Monitor closely for any worsening; and
5. If the reaction reoccurs, stop infusion. Study treatment will be discontinued;

- Grade 3 infusion-related reaction (CTCAE v5.0): Characterized as prolonged (e.g., not rapidly responsive to symptomatic medication and/or brief interruption of infusion); recurrence of symptoms following initial improvement; hospitalization indicated for clinical sequelae; or
- Grade 4 infusion-related reaction (CTCAE v5.0): Characterized as life-threatening consequences; urgent intervention indicated;

Treatment of Grade 3 or Grade 4 infusion-related reactions:

1. Stop the infusion immediately and disconnect infusion tubing from the patient;

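### Section 4.3.2: three of the five triggers that convene the DMC count only once the DMC has decided, so as worded the DMC must act before the event that convenes it

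*Combined protocol and SAP*

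**What the plan says.** The lead-in to Section 4.3.2 states that if any listed event is encountered, "the DMC will convene as soon as possible to determine if the study must stop enrollment". Five triggers follow.

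- Trigger 1 is an "SAE considered related to study drug". Trigger 2 is a related reaction of Grade 3 or higher. Neither mentions a DMC decision.
- Trigger 3 is met when two or more "patients are discontinued from treatment for safety reasons pertaining to study drug per DMC decision".
- Trigger 4 is met when two or more patients have similar SAEs or Grade 3 "AEs related to study drug per DMC decision".
- Trigger 5 is met when two or more "patients experience worsening of cytokine release syndrome related to study drug per DMC decision".

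Other sections settle the same matters without the DMC. Section 4.3 presumes that AEs are related unless they are clearly unrelated or clearly have another cause. Section 4.3.1 takes individual patients off dosing directly on protocol criteria. Section 8.2.3 has the Investigator classify relatedness as yes or no.

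**The concern.** A trigger for an unscheduled safety review should rest on something that can be observed without the body being called. Triggers 1 and 2 do. Triggers 3 to 5 make a DMC decision part of the condition, and the visible text does not say how the DMC would reach that decision before it meets.

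The value of a two-patient trigger is that it catches a pattern no single case would reveal: several patients coming off drug for a similar, individually moderate reason. If that trigger cannot fire by itself, the pattern may not reach independent review until the next scheduled meeting, while further patients are enrolled and dosed.

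**Working it through.** The plan gives no figure to reproduce, so the check sets the wording of the relevant sections side by side.

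**1. Count the qualified triggers.** Of five, two carry no DMC qualifier (1 and 2) and three do (3, 4 and 5): 2 + 3 = 5.

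**2. Ask what the qualifier could mean.**
- *The DMC decides whether a case is attributable to drug.* The DMC must then act before it is convened. Sections 4.3 and 8.2.3 place relatedness elsewhere.
- *The DMC decides that a patient discontinues.* Section 4.3.1 applies its criteria directly and names no DMC step.
- *The DMC decides whether enrollment stops.* This would remove the circularity, but the lead-in already gives the DMC that decision, and the phrase is attached to the events rather than to the stopping decision.

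No visible section makes the qualifier work as part of a trigger.

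**3. Find where it has an effect.** Trigger 4 needs two similar related SAEs or Grade 3 AEs. One related SAE already meets trigger 1. One related Grade 3 AE will generally meet trigger 2, since Section 8.2.1 treats an AE with a reasonably possible causal link as a reaction. So trigger 4 adds little, with or without the qualifier. Under Section 8.3, a related event that prolongs hospitalization or is judged an important medical event is an SAE, so it also falls under trigger 1. What is left for triggers 3 and 5 is clusters of related, non-serious events below Grade 3 that stop dosing.

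**4. Identify examples.**
- Section 4.3.1 stops dosing at or above "Grade 2 skin-related AEs". A Grade 2 cluster reaches only trigger 3.
- Section 4.3.1 stops dosing at or above "Grade 2 (CTCAE v5.0) cytokine release syndrome". A Grade 2 cluster reaches only triggers 3 and 5.
- Appendix C says of Grade 1 or 2 infusion-related reactions: "If the reaction reoccurs, stop infusion. Study treatment will be discontinued". That guidance is used at the treating physician's discretion. A cluster reaches only trigger 3.
- Section 4.3.1 also names related, clinically significant laboratory abnormalities. Its wording can be read with or without a Grade 3 floor; without one, these too may reach only trigger 3.

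The list is illustrative. Section 4.4, for instance, lets the Investigator end participation for a clinically significant AE, which may add others.

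**5. Compare with the scheduled reviews in Section 3.1.** Sentinel Cohorts 1 and 3 are each reviewed before the next cohort is dosed. Cohort 2 is reviewed when it is complete, so a cluster arising part-way through could wait until then. For Cohort 4 no later review is visible in Section 3.1 or the Synopsis, although the Section 3.1 bullet ends in a redaction.

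**The case against.** The strongest reply is that the governing text may be elsewhere. The Table of Contents lists Section 3.2 on the DMC and Section 3.2.1 on criteria for its review. Neither is in the public copy, and that absence is no fault of the plan. Section 3.2.1 may contain an unqualified trigger, or Section 3.2 may let the DMC judge cases between meetings. This stands, and it limits the point to the wording of Section 4.3.2.

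A second reply is that a decision is not a meeting: the DMC could rule on attribution case by case and convene once two cases count. That is workable in sequence, but it still needs the DMC to act first, by a route the visible text does not describe.

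A third is that the qualifier may be a deliberate filter, since investigators are blinded and half the patients receive placebo. That is a reasonable aim, and removing the phrase would give it up before convening. The convened DMC can still review attribution.

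Fourth, other safeguards are real. Cohorts 2 and 4 open only after the DMC has cleared sentinel patients in the same dosing group. Each affected patient stops dosing. The Investigator Agreement allows the sponsor to suspend enrollment at any time, and the investigator to do so to protect patients. These reduce the consequence, but none is a mandatory independent review of a cluster that appears after sentinel clearance.

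**Conclusion.** Wrong as written; minor. Three of five triggers carry the qualifier, and in practice it matters for two of them, triggers 3 and 5. The conclusion rests on reading the qualifier as part of each event and on the visible text alone.

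Three stronger inferences are tempting, and the documents do not support them.

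- *That the trial has no working cluster trigger, or that serious clusters would escape review.* The first cannot be said without Sections 3.2 and 3.2.1. The second conflicts with triggers 1 and 2, which call for a meeting after a single related SAE or a single related reaction of Grade 3 or higher.
- *That cohort size gives a number of patients exposed during the delay.* Triggers 3 to 5 are not limited to one arm or one cohort, and the visible text gives no event rates. Any such count would depend on where and when the two events fell.
- *That the affected event types can be listed completely.* The laboratory clause in Section 4.3.1 is ambiguous and Section 4.4 leaves room for judgement, so the examples above are only examples.

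**What to change.** Delete *per DMC decision* from triggers 3 and 5, and from trigger 4 for consistency, although the change there has little effect. Base relatedness for these triggers on the Section 4.3 presumption and the Investigator's assessment under Section 8.2.3. Leave the review of attribution and the decision on enrollment to the DMC once it has convened, as the lead-in already provides for enrollment. Check the result against Section 3.2.1 and align the two; if that section already has an unqualified trigger for these events, Section 4.3.2 should match it.

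The cost is amendment wording: three words in each of three triggers. The downsides are possibly an extra ad hoc DMC meeting and the loss of any intended DMC filter on attribution before convening. If the sponsor wants to keep such a filter, the protocol should say how and when the DMC applies it between meetings.
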